**Randomization:** Subjects will be randomized 1:1 into 2 groups. One group will receive TM home assessments/interventions for identification and reduction of asthma triggers in the home while the other group will receive standard of care asthma trigger education. Randomization will occur at the time of enrollment visit after consent and assent is obtained and initial demographic assessment is complete. All participants will receive the same asthma education and trigger reduction materials. For those randomized to TM, participants will receive TM assessment of their home as well as an Asthma Home-Assessment kit that will provide supplies to reduce asthma triggers in the home.

**The Role, Qualifications, and Expectations of the Home Visitor (HV):** The Home visitor (HV) is a frontline public health worker who is a trusted member of and/or has an unusually close understanding of the community served. The HV is in a unique position to partner with families due to living in the area they are serving or having similar cultural backgrounds. The person acting in this role will be responsible for performing standard of care trigger education and asthma TM home assessments to aide in the identification and reduction of exposure to indoor asthma triggers. The goal is to establish a trusting partnership with participants and family members by providing education and tools to maximize asthma control and management as well as model appropriate behavior standards and core values as exemplified by Arkansas Children's mission and vision statement. For the purpose of this pilot project, the HV will enter into a contract agreement with UAMS or the Arkansas Children's Research Institute (ACRI) for the period of the pilot project. A minimum of a high school education, with a Bachelor degree in a health or social science related field preferred. In addition, one year of experience in some type of home visiting related to health care. Asthma specific training will be provided in the amount of 10 hours by a Certified Asthma Educator. The HV will receive CITI training as well. The education materials are provided by the Association of Asthma Educators and a certificate of completion is awarded after post testing. The HV will be expected to carry out the asthma home assessment via TM consistent with the procedures listed below.

Title: Efficacy of Telemedicine Home Assessments for Identification and Reduction of

Asthma Triggers

PI: [name]

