**Table 1. Summary of Outcome Measures**

	Baseline	2months	4months	6months
Dust Mite Levels	X		X	
Asthma Control Test (ACT)	X	X	X	X
Healthcare Utilization	X	X	X	X
Satisfaction Survey	X	X	X	X
Information Recall Survey		X	X	X

**Primary Outcome Measure:** The primary outcome measure will be the mean difference in dust mite levels found in home dust samples at 4 months compared to baseline and between TM and standard of care groups. Dust mites (*Dermatophagoides farina* and *Dermatophagoides pteronyssinus*) are one of the most common triggers for asthma and are commonly found throughout homes. ELISA testing can be utilized to quantify household dust mite levels with levels  $\geq 2$  mcg/g considered positive. Prolonged reductions in household dust mite concentrations are associated with improved asthma outcomes.

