### **Data Analysis**

#### **Sample size:**

*Analysis for the primary endpoint:* The primary outcome measure is level of dust mite allergens as measured by the MARIA™ test data. Using a one-way analysis of covariance, we estimated that a sample size of 20 in each of the two groups will yield at least 96% power to detect a 4  $\mu\text{g/g}$  difference between group means assuming a common standard deviation of 2 and a two-sided significance level of 5%.

Title: Efficacy of Telemedicine Home Assessments for Identification and Reduction of

Asthma Triggers

PI: [name]

Institution: University of Arkansas for Medical Sciences (UAMS) and Arkansas Children's Hospital/Research Institute (ACH/ACRI)

Sponsor: UAMS Translation Research Institute (UAMS TRI)

**Analysis for the secondary endpoint:** To evaluate the secondary outcome variables, the distribution for each outcome (i.e. home environmental asthma trigger score (heat), ACT score, healthcare utilization, visit satisfaction, and education recall) will be first assessed with summary statistics and graphical measures. It is anticipated that the distribution for some of these variables will be positively skewed. In cases of non-normal data, a logarithmic or square root transformation will be applied to normalize the distribution of the data. Secondary outcomes will be assessed for significant differences between groups and from baseline to 4 months and 6 months using a univariate repeated measure analysis of variance that will include a time x group interaction.

All tests will be two-sided and assume a significance level of 5%. All statistical analyses will be performed using SAS software version 9.4 (SAS Institute Inc., Cary NC, USA).

**Missing data and general considerations:** All reasons for drop out and missing data will be documented and reported. Subjects will be replaced if the dropout rate exceeds the estimate of 10%.

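### The repeated-measures ANOVA for the secondary outcomes needs sphericity and has no correction; if correlation decays over visits and the pooled error is used, the 6-month between-arm contrast could exceed its 5% level.

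*Combined protocol and SAP*

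**What the plan says.** Under Data Analysis, in the paragraph on the secondary endpoint, the plan lists the heat score, ACT, healthcare utilization, visit satisfaction and education recall. It describes the comparison as one in which they are "assessed for significant differences between groups and from baseline to 4 months and 6 months". The method named for this is a repeated-measures ANOVA; the plan's words are "using a univariate repeated measure analysis of variance that will include a time x group interaction". The next paragraph adds: "All tests will be two-sided and assume a significance level of 5" per cent, with SAS 9.4 as the software. The only step that responds to the data is a log or square-root transformation for skewness.

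Table 1 schedules ACT, utilization and satisfaction at baseline, 2, 4 and 6 months. Education recall has no baseline. The Outcome Measures section ties the heat score to home visits in the telemedicine (TM) group. Under Secondary Outcome Measures, baseline utilization looks back 12 months, while later visits count only events since the previous contact. No within-child correlation or standard deviation is given for any secondary outcome.

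**The concern.** The univariate form of repeated-measures ANOVA estimates a single within-child error from all visits together. That error suits every contrast only under sphericity. Equal variances with equal correlations are enough for sphericity, but they are not the only way to satisfy it.

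The changes the plan names run from baseline to 4 and to 6 months, and baseline to 6 months is the widest gap in the schedule. If visits further apart are less alike, the 6-month change is more variable than the average between-visit change. A pooled standard error is then too small for it. This arises with complete data and has nothing to do with dropout.

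ACT and utilization carry Hypothesis 2, so a 6-month difference in asthma control could be called significant more often than stated, with an interval that is too narrow. The documents also give a specific reason to doubt equal variances for utilization: its baseline window is 12 months and its later windows are about 2 months.

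**Working it through.** **Inputs from the plan.** 20 children per arm, 1:1, two-sided 5%. The analysis sentence names baseline, 4 and 6 months; Table 1 adds 2 months. Both sets are worked.

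**Assumed, because the plan is silent.** Unit variance at each visit; correlation rho per 2 months of 0.4, 0.6 or 0.8, falling geometrically; complete, normal data; no treatment effect.

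**The plan's 5% first.** In a simulation of this ANOVA (100,000 trials per scenario) with equal variances and equal correlations, the pooled-error baseline-to-6-month contrast was significant in 5.00% of trials with four visits and 4.98% with three. The stated level is right when sphericity holds.

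**Formulas under decay.**
- Variance of a change over k two-month steps: V(k) = 2(1 - rho^k).
- The pooled error puts P, the mean of V over all visit pairs, in place of the contrast's own V.
- Large-sample level: 2 x Pr(Z > 1.96 x sqrt(P/V)).

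**Example: four visits, rho 0.6.** V(1) = 0.8 (three pairs), V(2) = 1.28 (two pairs), V(3) = 1.568 (one pair).
- P = (3 x 0.8 + 2 x 1.28 + 1.568)/6 = 1.088.
- 6 months: sqrt(1.088/1.568) = 0.833; 1.96 x 0.833 = 1.633; level 10.3%.
- 4 months: sqrt(1.088/1.28) = 0.922; 1.96 x 0.922 = 1.807; level 7.1%.

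| Visits (months) | rho | P | V, 6 months | SE ratio, 6 months | Level, 6 months | Level, 4 months |
|---|---|---|---|---|---|---|
| 0, 4, 6 | 0.4 | 1.584 | 1.872 | 0.920 | 7.1% | 5.7% |
| 0, 4, 6 | 0.6 | 1.216 | 1.568 | 0.881 | 8.4% | 5.6% |
| 0, 4, 6 | 0.8 | 0.699 | 0.976 | 0.846 | 9.7% | 5.4% |
| 0, 2, 4, 6 | 0.4 | 1.472 | 1.872 | 0.887 | 8.2% | 6.7% |
| 0, 2, 4, 6 | 0.6 | 1.088 | 1.568 | 0.833 | 10.3% | 7.1% |
| 0, 2, 4, 6 | 0.8 | 0.603 | 0.976 | 0.786 | 12.4% | 7.3% |

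The 6-month standard error is therefore 8-15% too small with three visits and 11-21% too small with four.

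**Simulation at the plan's sample size.** For rho 0.6 and 0.8 the pooled 6-month contrast ran at 8.6% and 9.8% (three visits) and at 10.4% and 12.4% (four visits), in agreement with the table.

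**Other patterns, pooled 6-month contrast (four visits; three visits).**
- Random slope: 7.0%; 6.5%.
- Equal correlation 0.5, baseline SD doubled: 10.9%; 8.5%.
- Equal correlation 0.5, baseline SD halved: 3.5%; 4.0%.
- Baseline and 6 months the most alike: 1.4%; 1.8%.

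**The time x group test and the remedies.** Over all scenarios the uncorrected time x group test ran at 5.0-7.0%, and at 4.5-5.0% with the Greenhouse-Geisser correction. The 6-month contrast with its own error term ran at 4.9-5.1% in every scenario.

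**The case against.** The strongest reply is that the plan does not commit to what is being criticised. It names a model and an interaction but no error term for any follow-up contrast. An analyst who gives each contrast its own error gets 5% whatever the correlations. "Univariate" might only mean one outcome at a time, and the comparison from baseline might mean change within an arm. The test that is named, the time x group interaction, is only mildly affected. If the contrast were read only after a significant interaction, it would run at 0.5-6.2%.

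Most of this stands, and it limits the claim. A reader might infer that the 6-month comparison is in fact tested at 7-12%. The documents do not support that: they give neither the correlation pattern nor the error term, and both size and direction depend on them. The upper end also needs the 2-month visit in the model, which the analysis sentence does not name; with the visits it does name, the 6-month figure stops at about 10% and the 4-month contrast is near nominal.

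A reader might also extend the problem to every secondary outcome. Recall has no baseline and heat is scored only in the TM group, so neither yields this between-arm contrast. For utilization the equal-variance calculation does not apply; the direction depends on whether counts or rates are analysed.

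What the reply does not remove is that the pooled error is what this form of ANOVA ordinarily uses, that nothing in the plan overrides it, and that no rule makes the contrasts wait for a significant interaction.

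**Conclusion.** The point holds in conditional form. The plan names an analysis that needs sphericity, gives reasons to doubt it (a 6-month span and unequal utilization windows), and provides no safeguard. For ACT and satisfaction, with correlation of 0.4 to 0.8 per 2 months decaying geometrically, equal variances and the pooled error, the 6-month between-arm contrast could run at about 7-10% with three visits or 8-12% with four. The 4-month contrast would be at about 5.5% or 7%, and the time x group test at about 5-7%. Under equal variances and correlations the level is 5%, and a smaller baseline variance takes it below 5%.

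The importance is modest: these are secondary outcomes in a 40-child pilot, and the primary dust mite comparison is untouched. It is still more than a missing detail, because the replacement holds 5% under every pattern tried and needs no new data.

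**What to change.** In the secondary-endpoint paragraph, drop the word univariate and state three things:

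1. Which visits enter the model, in particular whether the 2-month visit does.
2. That the between-arm differences in change from baseline to 4 months and to 6 months are each tested with their own error term. A mixed model with unstructured within-child covariance and Kenward-Roger degrees of freedom is an equivalent choice.
3. That, if the ANOVA is kept, the time x group test is reported with the Greenhouse-Geisser correction.

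The cost is a sentence or two, using standard options in the named software, with no added visits or data. A contrast with its own error has 38 degrees of freedom, against 2 x 38 = 76 (three visits) or 3 x 38 = 114 (four visits) for the pooled error. If sphericity does hold, the price is small: the critical t value is 2.02 instead of 1.99 or 1.98, so intervals are about 2% wider. Where correlation decays as assumed above, the standard error of the 6-month contrast rises by about 9-18% (1/0.920 to 1/0.846) with three visits or 13-27% (1/0.887 to 1/0.786) with four. That is the width the data warrant. The change does not settle how utilization over unequal windows should be compared.

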### **Ethical Considerations**

This study will be conducted in accordance with all applicable government regulations and UAMS research policies and procedures. This protocol and any amendments will be submitted and approved by the UAMS Institutional Review Board to conduct the study.

At the time of the detailed screening, the parent/caregiver/adult participant will indicate "Yes" on the eligibility document acknowledging verbal consent to complete the eligibility screener. The formal consent of each subject, using the IRB-approved consent form, will be obtained before the participant is submitted to any study procedures. All participants for this study will be provided a consent form describing the study and providing sufficient information in language suitable for participant to make an informed decision about their participation in this study. The person obtaining consent will thoroughly explain each element of the document and outline the risks and benefits, alternate treatment(s), and requirements of the study.

The consent process will take place in a quiet, private room and participants may take as much time as needed to make a decision about their participation. Participant privacy will be maintained and questions regarding study participation will be answered. No coercion or undue influence will be used in the consent process. Assent will be obtained from capable participants 7-17 years of age. This consent form must be signed by the participant or legally authorized representative, and the individual obtaining the consent. A copy of the signed consent will be given to the participant, and the informed consent process will be documented in each participant's research record.

**CONFIDENTIALITY:** The participant's records will be kept confidential with the exception of the Office for Human Research Protection (OHRP), UAMS IRB and other institutional oversight offices. The participant will be made aware that the Investigator

Title: Efficacy of Telemedicine Home Assessments for Identification and Reduction of  
Asthma Triggers

PI: [name]

Institution: University of Arkansas for Medical Sciences (UAMS) and Arkansas Children's Hospital/Research Institute  
(ACH/ACRI)

Sponsor: UAMS Translation Research Institute (UAMS TRI)

and HV are considered mandated reporters. As a mandated reporter the investigator and HV might be required to report any child abuse or neglect, as well as any intention of study participants for self-harm or harm of others. The Investigator and HV, if ordered to do so by a court of law, may also be required to disclose information the participant has provided.

### **Dissemination of Data**

We will protect the rights and privacy of all human subjects who participate in this research. The proposed research will include data from 40 children participating in the trial. The final dataset from the trial will include demographic, medical, and survey data from participants. The final dataset will be stripped of identifiers prior to release for sharing. Sharing of data will be accomplished by publication in the scientific literature, presentation at national scientific meetings, as well as communicating our findings to the public through the ACRI and UAMS Translational Research Institute websites.

Title: Efficacy of Telemedicine Home Assessments for Identification and Reduction of

Asthma Triggers

PI: [name]

Institution: University of Arkansas for Medical Sciences (UAMS) and Arkansas Children's Hospital/Research Institute (ACH/ACRI)

Sponsor: UAMS Translation Research Institute (UAMS TRI)

